Pregabalin vs. Gabapentin on Reducing Opioid Usage in Trauma Patients

NCT# 04705480

Protocol

IRB Approval Date: 07/22/2024

Title: Pregabalin vs. Gabapentin on Reducing Opioid Usage in Trauma Patients

Abstract

The pain following trauma can be difficult to manage because it can have more than one cause and differ from patient to patient. It is not uncommon for trauma patients to have localized pain related to their injuries coupled with a component of nerve pain. Pregabalin and gabapentin have both been effectively used in many studies to reduce opioid pain medication usage in patient care. Gabapentinoids (pregabalin and gabapentin) have historically been used to treat seizures, nerve pain, and anxiety. Current research, however, has successfully shown their effectiveness as pre- and post-operative pain medications. However, these studies have examined single-dose use of pregabalin/gabapentin in the management of postoperative pain and opioid consumption. As of yet, studies have not investigated the efficacy of multiple-dose administrations of these drugs on opioid consumption. The purpose of this study is to test the effectiveness of using multiple doses of pregabalin or gabapentin in combination with traditional opioid pain medications in order to decrease the amount of opioid pain medication usage in trauma patients. The primary outcome is to compare those receiving multiple doses of pregabalin vs. gabapentin vs. those receiving neither, and to determine daily average opioid requirement at 24 hour increments up to 7 days following initiation of study medication.

Word Count-163

Aims/Objectives

Primary Objective:

To determine if adding multiple doses of pregabalin or gabapentin upon admission will reduce opioid usage in trauma patients in the first 7 days of hospitalization or until discharge, if discharge < 7 days post-enrollment.

Secondary Objectives:

- I. To compare the change in documented incentive spirometry values from morning physical assessment among patients in each of the study groups who have at least 1 rib fracture. Decreased pain scores may correlate with improved incentive spirometry values, which may facilitate recovery from lung-related injury.
- II. To compare the proportion of patients requiring intubation among the study groups. Worsened pain is associated with respiratory distress which increases likelihood of intubation.

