- III. To assess effectiveness of pain control in each arm based on the average Numeric Pain Rating Scale score per 24 hours following randomization. This scale is a 10 point numeric scale that ranges from 0 that represents "no pain" to 10 which indicates the "worst pain imaginable."
- IV. To evaluate the differences among the study arms with respect to hospital length of stay and unplanned ICU admissions.

Background

According to the Centers for Disease Control and Prevention, trauma is the fourth leading cause of death in the United States.¹ It is a major cause of mortality throughout the world. There are many factors that can affect morbidity and mortality in trauma patients including pain. Trauma introduces acute as well as chronic pain into the lives of its victims.² In a study by Gross and Amsler, severity of pain before and at least 2 years after poly-trauma, which was defined as patients with a well-defined injury of at least two body regions, was evaluated. After 2.7 ± 0.9 years following injury, only 54% of poly-trauma patients were fully rehabilitated. An astonishing 59% had to undergo a change in their occupation due to their injury(s). In addition, 2 years post-trauma 85% of these patients continued to experience pain.³ Literature suggest that 22% of the population experience chronic pain and more than one third of those cases are the result of trauma. Forty-six percent of long-term survivors of high energy trauma report daily pain after their trauma as compared to only 5% before the accident.²

Improved pain management in trauma patients leads to increased comfort as well as reduced morbidity and improved long-term outcomes.⁴ Successful approaches for achieving adequate pain control can vary greatly from patient to patient resulting in difficulty with the routine provision of analgesia. Pain in trauma patients can be a complicated process. Injury severity is often related to the level of pain experienced by trauma patients; however, pain alone can complicate a patient's condition and potentially lead to further clinical deterioration of the patient. Baseline physiology of trauma patients can widely vary from young athletes to elderly frail adults. Presenting with multiple injuries, substance use disorder, delayed care, as well as psychological and emotional issues can further complicate the care process. Understanding pain in trauma patients and how to manage it is crucial to their care.

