the existing literature focuses on studies that have been conducted with patients having scheduled surgery and therefore administration of these drugs were standardized. Management of trauma patients on the other hand varies as patients present with varying injuries and requires individualized care plans. Accordingly, this study aims to reduce patients' consumption of narcotics in the hospital by utilizing multiple doses of adjunctive non-opioid analgesia for pain management in trauma patients.

Significance

The incidence of prescription opioid analgesic use has continued to increase and unfortunately the death rate from drug overdoses has shown a similar increase over the last several years. With alarming rates of drug-related deaths in West Virginia and the U.S. overall based on CDC data, it is crucial for clinicians to understand the impact that medical use of opioids may have on patients' mental and physical health. Especially, in the trauma patient population where opioid-based analgesia is commonly used to manage acute pain, it is important to treat the patient's pain without adding to the already growing problem. It is important for practitioners to be mindful and try to prescribe the lowest most effective dose needed to optimally control pain. Use of adjunctive analgesics may help lessen the amount of opioids prescribed and help the patient on their path of healing not just physically, but also emotionally and mentally.

Methodology

Study design

This will be a prospective, randomized trial with patients admitted to Charleston Area Medical Center's (CAMC) Trauma Services under the care of Nurse Practitioners (NPs) with attending supervision. Patients included in this study will be separated in three groups: Group A: Patients will be started on gabapentin upon admission after consented. They will receive 300 mg PO every 8 hours without dose titration. Group B: Patients will be started on pregabalin upon consent. They will receive 50 mg every 8 hours without dose titration. Group C: Patients in this group will be neither on gabapentin

nor pregabalin upon consent. In Groups A and B, patients with CrCl < 60mL/min will receive same dose given q12 hours. The q12 hour regimen may be increased to q8 hours if CrCl increases above 60mL/min during the 7 days study period or until discharge (if < 7 days post-enrollment).

Inclusion Criteria

1. NP service admissions
2. 18 year of age and older
3. Patients enrolled within 36 hours of admission

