4. Anticipated duration of hospitalization >24 hours from time of consent
5. Active order(s) for opioids in place at the time of enrollment

Exclusion Criteria

1. Clinician discretion based on patient care management
2. Intubated patients
3. Patients with epidural or peripheral nerve block
4. Patients with pregabalin/gabapentin as home medications
5. Patients receiving pregabalin/gabapentin upon admission
6. Traumatic brain injury patients
7. CrCl<30ml/min or on HD
8. Unable to take enteral medications
9. On Patient Controlled Analgesia (PCA)
10. Patients with complicated wound closure
11. History of epilepsy
12. Documented history of substance use disorder (this exclusion criterion was chosen to provide consistency among the study population as pain management may differ among these patients)

Setting

Charleston Area Medical Center's General Hospital, a Level 1 Trauma Center.

Sample Size

A sample size of 70 patient per study group which includes 10% attrition will be targeted (a total of 210 patients). This is based on Cohen's *d* formula with a significance of 0.05, 80% power and a medium effect size. Previous studies have evaluated the impact of single dose administration of pregabalin and gabapentin on pain and opioid consumption and were mostly conducted with patients having scheduled surgery. The current study, however, is designed to examine the effectiveness of multiple doses of these drugs in acutely injured trauma patients. Therefore, past reliable data could not be used for the power calculation for this study and Cohen's *d* coefficient was used for effect size. A medium effect size, which indicates a 69% difference between treatment and control groups was set by clinicians. For sample size estimation, instead of using effect size for the overall ANOVA which tests a general hypothesis we utilized effect sizes for the planned comparisons [(pregabalin vs. gabapentin); (pregabalin vs. neither pregabalin nor gabapentin); (gabapentin vs. neither pregabalin nor gabapentin)] using t-statistic.

Procedure/Protocols

Pre-intervention

- The clinical research coordinator will review the investigator's census on a daily basis in order to identify new admissions who may be study candidates.
- All patients who are eligible will be informed about the study. Patients with capacity who agree to participate will be consented using the consent form as written within 24 hours of admission. A note will be made in the patient's chart detailing the consent.

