 - Date & time of hospital admission and discharge
 - Comorbidities
- Urine and drug screen
- Admitting injury list
- Length of Stay
- Pre-existing (home) analgesic regimens
- Prior exposure of pregabalin or gabapentin
- Surgery dates and surgeries performed
- Inpatient analgesic exposure prior to enrollment (medications, dose, # of doses) and 7 days post-enrollment or until discharge (if < 7 days post-enrollment)

- Initial Incentive Spirometry value and 7 days post enrollment or until discharge (if < 7 days post-enrollment)
- Documented pain scores for each 24-hour period post-enrollment for 7 days or until discharge (if < 7 days post-enrollment)
 - Additional notation will be made to indicate the first pain score that coincides with the initiation of study medication
- Post-enrollment complications (unplanned intubation, unplanned ICU admission, incidence of VTE, infection, pneumothorax requiring chest tube placement, other)
- Post enrollment daily creatinine value from Basic Metabolic Panel
- Side effects including somnolence, dizziness, fatigue, ataxia, tremor, amnesia and others

Data Analysis

Descriptive analysis will be conducted for each variable in this study. Means and standard deviations or medians and interquartile ranges for continuous variables will be reported. For categorical variables, proportions and frequencies will be computed. To assess statistically significant difference between two cohorts, t-tests or Mann-Whitney U will be conducted for continuous variables. Categorical variables will be compared using chi-square or Fisher's Exact test. Outcome variables will be analyzed with ANCOVA or binary logistic regression controlling for differences in patient characteristics. A sub-analysis will be conducted by examining outcomes based on the number of days patients stay in the hospital post-enrollment. All comparisons will be performed at a level of significance of $p \leq 0.05$. Analysis will be done using 22.0SPSS version.

Subject Population

There are no known vulnerable participants to be included (specifically those under 18, prisoners, or those with pre-existing cognitive defects).

Benefits

Our study might show that pregabalin and gabapentin as adjunctive non-opioid analgesia may significantly reduce opioid usage in trauma patients, which will perhaps lessen complications related to use of opioids in trauma patients.

Risks and Discomfort

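### The primary opioid window has two conflicting start times, and the three planned pairs are each tested at 0.05 with no stated rule for the family

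*Combined protocol and SAP*

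**What the plan says.** **Start of the window.** The Abstract gives the primary outcome as "daily average opioid requirement at 24 hour increments up to 7 days following initiation of study medication". The Primary Objective looks at opioid use "in the first 7 days of hospitalization or until discharge, if discharge < 7 days post-enrollment", so its window opens at hospitalization while its discharge clause counts from enrollment. Under Study design, "Group C: Patients in this group will be neither on gabapentin" nor on pregabalin, so that arm has no study medication to initiate. Inclusion Criteria admit "Patients enrolled within 36 hours of admission". The Consent Process section also gives 36 hours, but the consent step under Procedure/Protocols gives 24.

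Other sections already use a later start. Study design ties all three groups to consent and describes a seven-day study period whose discharge clause counts from enrollment. Data Collection records analgesics for 7 days after enrollment and lists exposure before enrollment separately. Secondary Objective III assesses pain "based on the average Numeric Pain Rating Scale score per 24 hours following randomization".

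**Testing rule.** Sample Size states: "For sample size estimation, instead of using effect size for the overall ANOVA which tests a general hypothesis we utilized effect sizes" for the planned pairs, listed as "pregabalin vs. gabapentin); (pregabalin vs. neither pregabalin nor gabapentin); (gabapentin vs. neither pregabalin nor gabapentin". Data Analysis states: "All comparisons will be performed at a level of significance of" p ≤ 0.05. It names ANCOVA or logistic regression controlling for differences in patient characteristics, and a sub-analysis by days in hospital. No section makes the pairs conditional on an overall test, orders them, adjusts them, or says why none of this is needed. No section says how the 24-hour values become one primary test when a patient leaves before day 7.

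**The concern.** The two definitions of the primary outcome measure different things. The Abstract's start cannot be applied to one of the three arms. The objective's start brings in hours before enrollment, when the arms cannot yet differ, and so shrinks any true difference.

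Three pairs at 0.05 each, with no rule for the family, leave open what counts as a positive trial. Treatment is unblinded and opioid dosing is at the managing service's discretion. A window, summary or testing rule settled after the data are seen would therefore weaken the result.

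**Working it through.** **1. The plan's own sample size.** Inputs from Sample Size: alpha 0.05, power 80%, medium effect, 10% attrition. The value d = 0.5 is not printed. It is assumed from the word medium, and Φ(0.5) = 0.691 matches the 69% quoted there. Two-sided tests are also assumed.

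n per arm = 2(1.960 + 0.842)² / 0.5² = 62.8, rounded up to 63. Then 63 / 0.9 = 70, which is the plan's figure. A one-sided test would give 50, or 56 with attrition.

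**2. Cost of a hospitalization start.** If enrollment comes h hours after admission, a share h/168 of a 7-day window precedes any treatment. With even hourly use and unchanged SD, d becomes 0.5(1 − h/168). Power for one pair uses noncentrality d√(63/2), pooled variance and 3 × 62 = 186 df.

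| h (hours) | Share of window | d | Noncentrality | Power |
|---|---|---|---|---|
| 0 | 0% | 0.500 | 2.81 | 80% |
| 12 | 7.1% | 0.464 | 2.61 | 74% |
| 18 | 10.7% | 0.446 | 2.51 | 70% |
| 24 | 14.3% | 0.429 | 2.41 | 67% |
| 36 | 21.4% | 0.393 | 2.20 | 59% |

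The 12- and 18-hour rows are the mean delays if enrollment were spread evenly over 0–24 or 0–36 hours. The 24- and 36-hour rows need every patient to enroll at that time. The table is not an upper bound on dilution, because the window also closes at discharge: with 72 hours in hospital, 36/72 = 50%.

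**3. Error rates for the pairs.** One outcome, 63 evaluable per arm, no true differences:

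- One pair, in the direction of reduction: 2.5%.
- False reduction versus neither drug (two comparisons sharing Group C, correlation 0.5): 1 − Φ₂(1.96, 1.96; 0.5) = 4.54%.
- Any false difference among three pairs: P(studentized range of 3 means, 186 df > 1.973√2) = 12.2%.

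Simulation (400,000 trials) splits the last figure into 4.55% false reduction, 4.54% only a drug arm falsely higher than neither, and 3.12% pregabalin versus gabapentin alone. These sum to 12.21%.

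If the overall three-arm test must first be significant at 0.05, any false difference falls to 5.0% and false reduction to 2.1%. When only one pair is truly null (the other two differing by d = 0.3, 0.5 or 1.0), its false-difference rate stays between 4.2% and 5.0%. Power for one pair at d = 0.5 goes from 79.7% to 75.3% if the third arm equals either member of the pair, or to 69.1% if it lies midway.

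**4. Averaging over each patient's own days.** Secondary Objective IV compares length of stay between arms, so the number of days averaged may differ by arm. In an illustration with every input assumed (use falling evenly from 7 to 1 units over days 1–7, between- and within-patient SD 2, stays of 2–7 days, no drug effect), the false-difference rate for the raw mean, even with the overall test first, is:

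- equal stays: about 5%
- drug arms' mean stay 0.2 days shorter: 5.2%
- 0.4 days shorter: 7.4%
- 0.83 days shorter: about 15%

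A repeated-measures model with study day as a factor gives 4.6% in the last case.

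**The case against.** The strongest reply on the window is that the plan already runs on enrollment. Study design gives Group C a usable index time at consent, Data Collection counts 7 days after enrollment, and the objective's own discharge clause does the same. That stands. A reader might infer that pre-enrollment opioids will be counted as outcome, or that Group C cannot be followed on a common clock. The documents do not support either reading: no section plans to count those opioids as outcome, and they are listed separately. What remains is that both formal statements of the primary outcome say something else. Nor should 59% power be read as expected, since it needs every patient to enroll at 36 hours.

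On multiplicity, the reply is that control across three pre-specified pairs is partly convention, and that ANCOVA could supply an overall test. Both points stand. A reader might also take 12% as the risk of falsely claiming that a drug reduces opioid use. The figure for that claim is 4.5%; the rest of the 12% concerns other differences. What is missing is a statement of the rule.

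On the summary measure, a per-patient daily average analysed by ANCOVA is a legitimate reading of the plan. A reader might infer that it is necessarily biased. It is not if stays are similar, and the documents give no expected difference in stay. A repeated-measures model also changes the question, because it estimates use as if patients had stayed.

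**Conclusion.** The concern holds as a needed clarification of the primary outcome and its testing rule. It is not an error in the sample size, which reproduces.

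The two start times conflict, and neither matches the enrollment start used elsewhere. Following the objective literally would bring power for one pair down from 80% to between about 74% (enrollment at 12 hours) and 59% (36 hours), with greater dilution for short stays. This rests on d = 0.5, even hourly use, unchanged SD and a full 7-day window.

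With no rule for the pairs, the false-reduction risk versus neither drug is about 4.5% instead of 2.5%, and the risk of any false difference is about 12%. These figures assume two-sided tests, equal arms, no true differences and one test of one outcome. They are a floor if each 24-hour increment is also tested.

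**What to change.** 1. In the Abstract and Primary Objective, start the primary opioid window at randomization in all three arms, ending at day 7 or discharge. Do not count pre-enrollment opioids as outcome. Reconcile the 24- and 36-hour consent limits.
2. Name one primary summary of the 24-hour values. Include pre-enrollment opioid exposure, already collected, as a pre-specified ANCOVA covariate, rather than choosing covariates by observed differences. Add a repeated-measures model with study day as a factor, at least as a sensitivity analysis. State that it estimates use as if patients had stayed and assumes that discharge is explained by recorded data.
3. State the pairwise rule. A low-cost option is to test the overall three-arm effect first at 0.05, then the pairs at 0.05 only if it is significant. If adopted, restate pairwise power as about 75% (about 69% if the third arm lies midway) at 63 evaluable per arm and d = 0.5, with no added enrolment. For comparison, Bonferroni over three pairs would leave about 65–66% power, or need 84–86 evaluable per arm.
4. Report day-by-day differences and the sub-analysis by days in hospital as descriptive.

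Enrolment, treatment and data collection do not change. The cost is a less favourable power statement than 80%, and early discharge may lower it further. In an illustration of the repeated-measures model with the overall test first, stays spread evenly over 2–7 days and day-to-day correlation 0.5 (both assumed), power is about 71%, or 64% with the third arm midway. Any gain from the covariate is unknown, because the documents give no correlation.

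### Five secondary endpoints across three arms are all tested at p ≤ 0.05 with no order, no condition on the primary result and no supportive label

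*Combined protocol and SAP*

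**What the plan says.** Under Aims/Objectives, four secondary objectives name five endpoints:

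- I: change in incentive spirometry, in patients with at least one rib fracture.
- II: "To compare the proportion of patients requiring intubation among the study groups".
- III: "To assess effectiveness of pain control in each arm based on the average Numeric Pain Rating Scale score per 24 hours following randomization".
- IV: "To evaluate the differences among the study arms with respect to hospital length of stay and unplanned ICU admissions", which is two endpoints.

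The design has three arms: "Patients included in this study will be separated in three groups". Sample Size lists all three arm pairs as planned comparisons and bases the calculation on them instead of on an overall ANOVA.

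Data Analysis offers t-tests or Mann-Whitney U for two cohorts, chi-square or Fisher's exact test for categorical variables, and ANCOVA or binary logistic regression for outcomes. It also plans a sub-analysis by days in hospital. It then states: "All comparisons will be performed at a level of significance of $p \leq 0.05". The protocol contains no multiplicity adjustment, testing order, gate on the primary result, or exploratory or supportive label.

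**The concern.** Leaving secondary endpoints unadjusted is common and acceptable when the plan says that they are supportive. Here the only decision rule gives primary and secondary comparisons the same standing. If the opioid comparison is null, the rule still lets the trial report a significant effect on pain, spirometry, intubation, ICU admission or length of stay. A reader could not tell such a result from the yield to be expected of many tests. Pain is the most exposed endpoint: it is patient-reported, the trial is unblinded (Procedure/Protocols), and objective III is framed in terms of effectiveness.

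This point covers the secondary family only, not the primary opioid contrasts or their day-by-day testing.

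**Working it through.** **The plan's own figure.** Sample Size states "This is based on Cohen's *d* formula with a significance of 0.05, 80% power and a medium effect size" and "A medium effect size, which indicates a 69% difference between treatment and control groups was set by clinicians". Taking medium as d = 0.5 fits the stated 69%, since Φ(0.5) = 0.69. Assuming two-sided tests (sidedness is not stated):

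n per arm = 2 × (1.960 + 0.842)² / 0.5² = 62.8, so 63; 63 / 0.90 = 70.

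This reproduces "A sample size of 70 patient per study group which includes 10% attrition will be targeted (a total of 210 patients". It also shows that 0.05 is a level per comparison, applied in full to each pair.

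**Number of secondary tests.** Five endpoints × 3 pairs = 15. With one three-arm (omnibus) test per endpoint there are 5. With pain tested on each of seven days there are 4 + 7 = 11 endpoints, or 33 pairwise tests. The sub-analysis by days in hospital would add more and is not counted.

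**Simple bounds, no true effect anywhere.**

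- Expected false positives at nominal size: 15 × 0.05 = 0.75 (pairwise) or 5 × 0.05 = 0.25 (omnibus), whatever the correlation.
- At least one, if all tests were independent: 1 − 0.95^15 = 53.7%; 1 − 0.95^5 = 22.6%.

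The 53.7% is too high, because pairs share arms. Simulating one endpoint with three pairs gives 12.2%, not the 14.3% from 1 − 0.95³.

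**Simulation with shared arms and correlated endpoints.** Three equal arms, five endpoints with equal correlation within patient, no true effect, two-sided 0.05. Chance of at least one significant result:

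| Assumed endpoint correlation | 0 | 0.5 | 0.8 |
|---|---|---|---|
| All three pairs, five endpoints | 48% | 39% | 28% |
| The two drug-versus-neither pairs only | 38% | 31% | 22% |
| One omnibus test per endpoint | 23% | 19% | 13% |
| False benefit only, drug versus neither | 21% | 16% | 11% |

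**What lowers the figures.** Fisher's exact test is conservative for rare events. With 63 per arm, the three-pair false-positive chance for one binary endpoint is 0.9%, 3.4% and 6.0% at assumed event rates of 3%, 5% and 10%, against 12.2% at nominal size. Combining three continuous endpoints with two such binary ones, the latter treated as independent of everything else:

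- Rates 3% and 5%: 35% at correlation 0 among the continuous endpoints, 31% at 0.5.
- Rates 5% and 10%: 38% (38.5%) and 35%.

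**What raises them.** Pain tested daily, all pairs: about 50–62%, assuming day-to-day correlation of 0.6–0.8 and other correlations of 0.3–0.5.

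**The case against.** The strongest reply has four parts.

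*Pairwise testing of the secondaries is not stated.* The three pairs appear in the sample-size text. The secondary objectives speak only of differences among groups or arms, and ANCOVA or logistic regression could mean one three-arm test per endpoint. This stands, and it is why the omnibus range is given. The two-cohort tests in Data Analysis make pairwise testing the closer reading, but it remains an inference.

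*No single rate follows from the documents.* A reader might infer that the trial has a 30–40% false-positive chance. That band holds only for pairwise tests with moderately correlated endpoints or assumed rare-event rates. A reader might also set 39% against 0.05 and call it an eightfold breach. The 0.05 is a level per comparison, and the protocol promises no family-wise rate, so the two cannot be compared in that way.

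*Much of the figure is not false benefit.* It counts harm as well as benefit, and pregabalin versus gabapentin. False benefit against neither drug is 11–21%. Intubated and brain-injured patients are excluded, so intubation may be rare and add little. This stands, and it limits the size.

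*Primary and secondary objectives are already separated.* Nowhere does the plan say that a secondary result will support a claim if the primary fails; the only conclusion anticipated under Benefits concerns opioid use. It would be wrong to infer that such a claim is intended. But the separation into objectives has no consequence in Data Analysis, where the rule treats every comparison alike. The gap is in what the rule permits.

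**Conclusion.** The concern holds in limited form. Five secondary endpoints are compared among three arms at the full 0.05, with no order, no condition on the primary result and no supportive label. With no true effect, the chance of at least one significant secondary result is about 28–48% for pairwise tests, or 13–23% for one omnibus test per endpoint. These ranges rest on assumed equal endpoint correlations from 0.8 to 0, tests at nominal size, and pain analysed as one summary per patient.

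The conclusion does not depend on one number: even the lowest of these readings is more than twice what a single test at 0.05 would give. It affects how secondary results may be interpreted, not the sample size or the primary analysis. It is a cheap improvement in wording, not a flaw that undermines the trial.

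**What to change.** In Data Analysis, limit the p ≤ 0.05 rule for claims to the primary opioid analysis, and add:

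> *Secondary objectives I–IV are supportive; they will be reported as between-arm estimates with 95% confidence intervals, unadjusted for multiplicity, and no claim of effectiveness will be based on them alone.*

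Do not add a gate that lets one secondary be tested once the primary contrast is significant unless the plan first names which of the three primary contrasts opens it and how error across those contrasts is controlled. Without that, the gate is undefined.

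The cost is one or two sentences, with no new patients or data. The downside is that the trial gives up standalone significance claims on secondary endpoints.
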